The goal of this study is to investigate the risk of COPD exacerbations, community acquired pneumonia, and health care utilization in patients treated with Tio+Olo in comparison to patients treated with ICS/LABA/LAMA. All analyses will be conducted for the total population, as well as in sub-groups of patients under (1) high- or low risk of exacerbation based on previous history of exacerbations in the year preceding cohort entry (cut-off: 0-1 vs 2+ exacerbations [P07-11503], (2) circulating eosinophils (cut-off B-Eos 300 cells/uL, [P18-09975]), and (3) as an exploratory analysis, a combination of exacerbation history and circulating eosinophils.

Primary objectives:

The primary objective is to compare the effectiveness of new use of maintenance therapy initiation with the combination treatment Tiotropium and Olodaterol (Tio+Olo) compared with new use of LABA/LAMA/ICS combination in COPD as the time to the first COPD exacerbation.

Secondary objective:

The secondary objective is to assess the association between maintenance therapy initiation with the combination treatment (Tio+Olo vs any LABA/LAMA/ICS combination in COPD and time to community acquired pneumonia.

Exploratory objective:

To assess differences between Tio+Olo vs any LABA/LAMA/ICS in all-cause and COPD-specific healthcare utilization and cost overall and by care setting.

Proprietary confidential information © 2019 Boehringer Ingelheim International GmbH or one or more of its affiliated companies

7. **RESEARCH METHODS**

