7.1 STUDY DESIGN

Population-based incident new-user cohort design.

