7.3 SUBJECTS

The study cohort will be formed based on the following entry criteria.

Inclusion Criteria:

- 1. At least one prescription for Tio+Olo or a LABA/LAMA/ICS combination between 1 January 2013 and 31 March 2019.
 - a. For Tio+Olo users, the first dispensing of Tio+Olo will be defined as the index date.
 - b. LABA/LAMA/ICS use can occur either in free or fixed combinations. The first date when all three medications are used based on either concurrent or overlapping dispensings in the pharmacy claims data will be defined as the index date.
- 2. At least one diagnosis of COPD at any time prior to the index date.
- 3. At least one year of continuous medical and pharmacy health plan eligibility prior to the index date will be required to allow a baseline period for the covariates and identification of new use of the study drugs.

Exclusion Criteria:

- 1. To increase the likelihood of a true diagnosis of COPD, we will exclude:
 - a. All patients less than 40 years of age on the index date, and
 - b. All patients with a diagnosis of asthma in the year prior to the index date
- 2. To limit the population to those without severe lung compromise outside of COPD, we will exclude individuals with lung cancer, interstitial lung disease, or lung transplant identified at any time prior to the index date
- 3. To restrict the cohort to new users of Tio+Olo or LABA/ICS, we will exclude any individual with use of either Tio+Olo, LABA/ICS, or LABA/LAMA/ICS combination therapy in free or fixed form for at least one year prior to the index date.

Outpatient laboratory data is available for a subset of patients. Some analyses will be further restricted to the subset of the population with at least one laboratory result showing circulating eosinophil levels within six months before the index date.

Individuals in the study cohort will be followed from the index date until the earliest of the date of a switch in treatment, addition of ICS for the Tio+Olo group, discontinuation of

COPD treatment, the end of the study period, or the end of continuous health plan eligibility. Main analyses will be further limited to the first year after cohort entry, with sensitivity analyses considering all available data.

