7.4.3 Covariates

Patient characteristics at baseline will be assessed for Tio+Olo and LABA/LAMA/ICS user overall and stratified by history of exacerbation, circulating eosinophils, subgroups defined by both exacerbation and eosinophil levels.

We will identify and describe the following demographic characteristics as of the index date:

- Sex
- Age (years, as both a categorical and a continuous variable)
- Calendar year of cohort entry

Proprietary confidential information © 2019 Boehringer Ingelheim International GmbH or one or more of its affiliated companies

- Season of index date (winter, spring, summer, fall)
- US census region of residence
- Insurance type (e.g., Commercial, Medicare)

Additional characteristics will be defined during the 12-month pre-index baseline period:

- Number of previous COPD treatments
- Specific previous COPD treatments
 - LAMA monotherapy
 - LABA monotherapy
 - ICS monotherapy
 - LAMA/ICS combination therapy
 - LABA/ICS combination therapy
- Previous acute COPD exacerbation (measured both overall and in the 30 days prior to cohort entry), categorized as 0, 1, or 2+.
 - All exacerbations (Moderate+Severe)
 - ED visits or dispensings of inhaled corticosteroids/antibiotics (Moderate)
 - Hospitalizations (Severe)
- Use of other respiratory drugs in the 12-month pre-index period:
 - Short-acting beta-agonists
 - Anticholinergics
 - Methylxanthines
 - Muscarinic antagonists
 - Short-acting muscarinic antagonists
- Use of antibiotics for a respiratory condition (e.g., azithromycin)

Chronic comorbidities will be defined using diagnoses identified during all available data prior to the index date, and will include:

- Cardiovascular disease
- Charlson comorbidity index
- Diabetes
- Thyroid disease
- Renal failure
- Autoimmune disease
- Pneumonia
- Obesity*
- Alcohol use disorder*
- Tobacco use or cessation counselling*
- Cancer (excluding basal cell carcinoma)
- * We anticipate limited capture of lifestyle variables known to be risk factors and potential confounders, including obesity, smoking status and excessive alcohol consumption. Although we will describe them as identified in the HIRD, bias analyses to examine the extent to which residual confounding may impact results are also planned.

Additionally to the covariates defined above, we will use the high-dimensional approach to identify variables entering a time-conditional propensity score.

Boehringer Ingelheim	

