ANNEX 3.1: DEFINITION OF STUDY EXPOSURES

Medication	HCPCS	GPI
LABA (single)		
Indacaterol		44201042X
Salmeterol		4420105810X
Formoterol	J7605, J7606, J7640, O4099	44201027X 44201012102520
Olodaterol		44201052X
LAMA (single)		
Tiotropium	1	44100080X
Aclidinium		44100007X
Glycopyrronium	J7642, J7643	44100020X
Umeclidinium		44100090X
Revefenacin		44100075002020
ICS (single)		4440X
		4220X
Fluticasone	J7641	44400033X
Budesonide	J7626, J7627, J7633, J7634	44400015X
Beclomethasone	J7622	42200010x
		44400010x
Mometasone		42200045101820
		44400036X
Flunisolide	J7641	44400030X
Ciclesonide		4440001700x
Dexamethasone		4440002010x
Triamcinolone	J7683, J7684	4440004020x
LABA/LAMA		
Formoterol/glycopyrroni um		44209902543220

c30699487-01

Proprietary confidential information © 2019 Boehringer Ingelheim International GmbH or one or more of its affiliated companies

Medication	HCPCS	GPI
Indacaterol/glycopyrroni um		44209902600110
Vilanterol/umeclidinium		4420990295X
Olodaterol/tiotropium		4420990292X
LABA-LAMA-ICS		
Fluticasone furoate/umeclidinium/vil anterol		44209903408020

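### Prior use of LABA/LAMA combinations other than Tio+Olo is neither washed out nor named as a propensity-score covariate

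*Combined protocol and SAP*

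**What the plan says.** Section 7.1 describes a "Population-based incident new-user cohort design", and the primary objective in Section 6 concerns "new use of maintenance therapy initiation with the combination treatment Tiotropium and Olodaterol".

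Section 7.3 sets entry. For one arm, "For Tio+Olo users, the first dispensing of Tio+Olo will be defined as the index date", with no condition on earlier dual bronchodilator use. The triple arm is indexed on the first day all three classes are in use, by concurrent or overlapping dispensing, in free or fixed form. Exclusion 3 opens with "To restrict the cohort to new users of Tio+Olo or LABA/ICS" and then says "we will exclude any individual with use of either Tio+Olo, LABA/ICS, or LABA/LAMA/ICS combination therapy in free or fixed form". The look-back is set at a minimum of one year before index.

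Annex 3.1 gives codes for three fixed LABA/LAMA products besides Tio+Olo, among them "Vilanterol/umeclidinium", and for the single agents that could form a free pair.

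Under "Specific previous COPD treatments", Section 7.4.3 names LAMA, LABA and ICS monotherapy, LAMA/ICS and LABA/ICS. It also lists the number of previous COPD treatments, exacerbation history, and a high-dimensional search for further propensity-score variables.

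**The concern.** A new-user design aims to start follow-up when treatment really changes. For a patient moving from vilanterol/umeclidinium to Tio+Olo, the two drug classes simply continue. Such a patient has already tolerated dual bronchodilation, and may have switched for a reason related to exacerbation risk. A patient on the same product who moves to triple therapy has been escalated, and escalation often signals worse control. If these histories differ between arms and are not balanced, the primary hazard ratio reflects treatment history as well as treatment. The codes needed to identify these patients are already in the protocol, but no entry criterion or named covariate applies them to baseline history.

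**Working it through.** **Step 1. Set exclusion 3 beside the covariate list.**

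| Regimen in the year before index | Washed out (7.3, exclusion 3)? | Named prior treatment (7.4.3)? |
|---|---|---|
| Tio+Olo | Yes | No, not needed |
| LABA/LAMA/ICS | Yes | No, not needed |
| LABA/ICS | Yes | Yes, but empty once the exclusion is applied |
| LAMA/ICS | No | Yes |
| LAMA, LABA or ICS alone | No | Yes |
| LABA/LAMA other than Tio+Olo | **No** | **No** |

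Only the last row is open on both counts.

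**Step 2. Trace two patients.**

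- Eleven months of vilanterol/umeclidinium, then a first Tio+Olo dispensing: none of the excluded regimens has been used, so if the other criteria are met the patient enters the Tio+Olo arm.
- The same history, then a switch to fixed triple therapy or the addition of an ICS: under the overlap rule in 7.3 the patient enters the triple arm. The abstract's inclusion criteria instead speak of starting on the same date. Read strictly, that would bar the separately added ICS, but neither the switch to a fixed triple nor the switch to Tio+Olo.

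**Step 3. Illustrate the size.** The documents give no share of prior LABA/LAMA users; the feasibility table in Section 7.7 has no such row. Let f be the share in the Tio+Olo arm, g the share in the triple arm, and k the hazard of such patients relative to others, the same in both arms. With a true hazard ratio of 1, a low event rate and no adjustment, the triple-versus-Tio+Olo hazard ratio is multiplied by

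(1 + g(k − 1)) / (1 + f(k − 1)).

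All inputs are assumed:

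| f | g | k = 0.8 | k = 1.5 |
|---|---|---|---|
| 10% | 5% | 0.99/0.98 = 1.01 | 1.025/1.05 = 0.98 |
| 30% | 10% | 0.98/0.94 = 1.04 | 1.05/1.15 = 0.91 |
| 10% | 30% | 0.94/0.98 = 0.96 | 1.15/1.05 = 1.10 |
| 50% | 10% | 0.98/0.90 = 1.09 | 1.05/1.25 = 0.84 |

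The first three rows span about 0.91 to 1.10. Only the extreme last row goes further. The sign depends on which arm holds more of these patients and on whether their risk is lower or higher.

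**Step 4. What a restricted analysis costs in power.** Section 7.7 cites over 90% power for a hazard ratio of 0.85 with 2,000 patients per cohort, without an event rate or alpha. By Schoenfeld's formula with two-sided alpha of 0.05 (assumed), 90% power needs 4 × (1.960 + 1.282)² / (ln 0.85)² ≈ 1,592 events. That is 39.8% of 4,000 patients, so the figure is attainable but cannot be confirmed.

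For the present cohort I take 5,469 Tio+Olo and 42,227 triple patients from Section 7.7. With D total events and a the Tio+Olo fraction, power = Φ(√(D·a(1 − a)) × |ln 0.85| − 1.96). Shares removed and event proportions are assumed:

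| Removed (Tio+Olo / triple) | Patients left | 10% with event | 20% with event |
|---|---|---|---|
| 0 / 0 | 5,469 / 42,227 | 94.7% | 99.9% |
| 30% / 10% | 3,828 / 38,004 | 85.8% | 99.0% |
| 50% / 20% | 2,734 / 33,782 | 73.4% | 95.5% |

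These ignore the precision lost to weighting, and the Section 7.7 table shows no rows for the asthma and lung-disease exclusions, so actual power would be somewhat lower.

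**The case against.** The plan defines new use by study drug, not by class. Inclusion criterion 3 sets the baseline year to identify new use of the study drugs, and Section 7.4.1 names these as Tio+Olo and LABA/LAMA/ICS. On that definition a vilanterol/umeclidinium user starting Tio+Olo is a new user. Patients with earlier COPD treatment are expected, since several earlier regimens are covariates. This stands: a reader might infer that the eligibility rule contradicts the incident new-user label, and the documents do not support that.

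A reader might also infer that step-ups from dual therapy in general enter the triple arm. They do not. Step-ups from Tio+Olo or LABA/ICS within the year are barred. What remains open is other LABA/LAMA, and LAMA/ICS, which is at least a named covariate.

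The plan also has partial protection: the treatment count, monotherapy flags that may pick up a free pair, exacerbation history over 12 months and over the last 30 days, data-derived variables, and a 0.10 standardized-difference threshold with further refinement. This stands in part. A count does not identify a regimen, monotherapy flags do not define a fixed dual product, and the balance check is assured only for variables that are named or selected.

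Finally, a systematic inflation of the hazard ratio by 10% to 20% can be produced: shares of 25% and 10% with hazards of 0.8 (Tio+Olo) and 1.5 (triple) give 1.05/0.95 = 1.105, and 40% and 20% give 1.10/0.92 = 1.196. These assign the same history opposite effects in the two arms, on no documentary basis. A common hazard of 1.2 with the first shares gives 1.02/1.05 = 0.971, on the other side of 1.

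**Conclusion.** The gap is real and limited. It rests on the text of Sections 7.3 and 7.4.3 and Annex 3.1 and needs no assumption. How many patients it admits, and which way and how far they would move the result, cannot be determined from the documents. A shift of roughly 10% either way is what moderate assumed inputs give before adjustment; the planned propensity score may remove some or most of it. Against the 15% difference discussed in Section 7.7, that is enough to justify an inexpensive safeguard. It does not show that the primary estimate is biased, or that all prior LABA/LAMA users must be excluded. Severity: should-fix.

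Some wording suggests text carried over from another comparison: exclusion 3 refers to new users of LABA/ICS, and Sections 7.4.2.1 and 7.9.1 also name LABA/ICS where the comparator is triple therapy. That may explain the omission, but the documents do not confirm it.

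**What to change.** 1. In Section 7.4.3, add LABA/LAMA combination therapy in the 12-month baseline, fixed or free, using the Annex 3.1 codes, to the specific previous treatments. Force it into the propensity score and apply the existing 0.10 balance check to it.
2. Report the number and percentage of patients with this history in each arm, before and after weighting.
3. Repeat the primary analysis excluding patients with prior-year LABA/LAMA use, refitting the propensity score in the restricted cohort.
4. Reconcile the abstract's same-date wording with the overlap rule in Section 7.3, and the LABA/ICS wording in exclusion 3 with the LABA/LAMA/ICS comparator.

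The cost is programming and a few lines of text. The main cohort is unchanged; only the restricted analysis loses precision. Extending exclusion 3 to all LABA/LAMA is an option for the sponsor. It would give a cleaner class-level new-user cohort, but a smaller and less representative one, and would bear most on small strata such as the 481 Tio+Olo patients with low exacerbation history and eosinophils of 300 cells/µL or more.

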7.4 VARIABLES

7.4.1 **Exposures**

The exposure measures are based on pharmacy dispensings of the study medications, namely Tio+Olo and LABA/LAMA/ICS combination therapy. As described in the data analysis section, the as-treated analysis, which is the main analysis, will consider continuing exposure of the initial treatment of Tio+Olo or LABA/LAMA/ICS within the treated groups defined by the days supply recorded at the time of pharmacy dispensing, allowing for a gap between dispensings of up to 15 days. This gap is allowed in consideration of plausible delays in obtaining medication refills and continued use beyond the days supplied where medication has been missed due to imperfect adherence, and will be varied in sensitivity analyses (see Section 7.9.2). Codes used to identify study medications are included in Annex 3.1.

The treatment segment ends at the earliest of the following events:

- 1. Fifteen days after the end of the observed days supply for the medication received on the index date without a subsequent dispensing of COPD medication (i.e., discontinuation)
- 2. Initiation of triple therapy (i.e., addition of ICS to Tio+Olo or a LAMA to LABA/ICS (i.e., treatment escalation, applies to Tio+Olo only)
- 3. Any other change in use of study medication by active ingredient, inclusive of a change to a different combination therapy, change from a fixed form to a free form combination therapy, or a change from combination therapy to monotherapy (i.e., switch)

Changes in dose for medications started on the index date will not impact the end of the treatment segment. Codes used to identify study medications are included in Annex 3.1.

7.4.2 **Outcome(s)**

7.4.2.1 **Primary outcome(S)**

The primary outcome event for effectiveness is the first COPD exacerbation to occur after cohort entry. The event is defined as follows:

- Severe exacerbation: •
 - Hospitalization with a principal discharge diagnosis of COPD.
 - Moderate exacerbation:
 - An ED visit with a discharge diagnosis of COPD and/or
 - Dispensing of an antibiotic and an oral corticosteroid on the same day

Time to the first COPD exacerbation will be measured from cohort entry until the occurrence of a hospitalization for COPD (severe exacerbation) or ED visit for COPD with the prescription of an antibiotic and/or an oral corticosteroid on the same day (moderate exacerbation). Severe and moderate exacerbations will be considered as a composite for main analyses. Sensitivity analyses will stratify by exacerbation severity.

Although there is precedent for defining moderate exacerbation based on use of antibiotics for a respiratory infection without requiring concomitant oral corticosteroids, we have chosen

a more restrictive definition of exacerbation. Because diagnoses listed on outpatient claims often correspond to a patient's past medical history in addition to acute problems, we expect limited ability to capture the indication for which antibiotics are prescribed. As such, including antibiotics alone as a case definition for exacerbation would introduce potentially substantial misclassification of outcome where antibiotics were truly given for non-respiratory infections. Given that our analyses will yield estimates on a ratio measure, non-differentially reduced sensitivity is a less important threat to validity than reduction of outcome specificity, which produces an expectation of bias towards the null hypothesis. In order to test our assumptions that the sensitivity of our outcome definition is not differential between the Tio+Olo and LABA/ICS groups, we would produce counts of patients with antibiotics alone during follow-up, and determine whether the proportion of potential exacerbations that we excluded through this design decision is comparable across groups.

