Population:	The cohort will consist of all patients in the HIRD with a diagnosis of COPD who received Tio+Olo or combination LABA/LAMA/ICS treatment from 1 January 2013 until 31 March 2019 (or the most recent date available at the time of cohort extraction). To increase the likelihood of a diagnosis of COPD and decrease the likelihood of including misdiagnosed asthma patients, we will only include patients 40 years of age or older on the index date and exclude all patients with a diagnosis of asthma within the year prior to the index date or lung cancer, interstitial lung disease, or lung transplantation at any time prior to the index date. Patients will have at least one year of medical history information prior to the cohort entry date to allow the identification of new use and the measurement of baseline covariates. Patients will be followed until switching to the other treatment, other changes in therapy, discontinuation of COPD treatment, the end of the individual's health plan eligibility, or the end of the study period, whichever occurs first. Main analyses will be limited to the first year following the index date.		
Study data source:	showing eosinophil levels will occur for relevant sensitivity analyses.		
			رب ال
Expected study size:	Overall:		
	New users of Tio+Old	p: 5,458	
	New users of LABA/I	LAMA/ICS: 42,361	
	With eosinophil result	t data:	
	New users of Tio+Old	p: 2,198	
	New users of LABA/I	LAMA/ICS: 15,712	
Main criteria for inclusion:	- New users of Tio+O either as a fixed-dose (LABA/ICS + LAMA March 2019.	lo on the same date or of LABA combination (LABA/LAMA/IC , etc), on the same date between	, LAMA and ICS, S) or free combination a January 2013 and
	index date	prior to first maintenance inhale	$r and age \ge 40$ years at

data.

SI Study Number 1237-0094 c30699487			c30699487-01
Proprietary confidential inf	formation © 2019 Boehringer II	ngelheim International GmbH or one or mor	e of its affiliated companies
Name of company:			Boehringer
Boehringer Ingelheim			Ingelheim الا
Name of product: Spiol	to		
Name of active ingredie	nt:		
Tiotropium bromide +	Olodaterol		
Protocol date:	Study number:	Version/Revision:	Version/Revision date:
12 December 2019	1237-0094	1.0	NA

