7.9 DATA ANALYSIS

7.9.1 Main analysis

All analyses will be presented for each group (Tio+Olo vs LABA/LAMA/ICS) overall and stratified as follows:

- History of exacerbation: 0 inpatient and 0-1 outpatient events
- History of exacerbation: 1 + inpatient or 2 + outpatient events
- Circulating eosinophils: B-Eos < 300 ug/mL
- Circulating eosinophils: B-Eos 300 ug/mL+
- History of exacerbation: 0 inpatient and 0-1 outpatient events & circulating eosinophils: B-Eos < 300 ug/mL
- History of exacerbation: 0 inpatient and 0-1 outpatient events & circulating eosinophils: B-Eos 300 ug/mL +

We will first describe formation of the study cohort. Patient characteristics at baseline in patients treated with Tio+Olo and patients treated with LABA/LAMA/ICS will be described using standard descriptive statistics. Because eosinophil levels may vary based on exacerbation, we will also provide a count and percentage of the number of individuals whose eosinophil results were recorded within 30 days of an exacerbation event.

High-dimensional propensity scores including both pre-specified and data-derived variables will then be calculated. We will use fine stratification and reweighting of the exposure propensity score to control for measured covariates [R19-3030]. Balance of patient characteristics between the cohorts will be described before and after propensity score application and compared using standardized differences (in the crude population and the reweighted pseudo-population). Standardized differences greater than 0.10 (10%) will be taken to indicate imbalance and further refinement approaches will be applied.

For the analysis of the primary objective, a Cox proportional hazard regression model will be used to perform an as-treated analysis that assesses the effect of current use of LABA-LAMA-ICS combination versus the Tio+Olo combination on the risk of a first COPD exacerbation. It will provide an estimate of the hazard ratio (HR) of a COPD exacerbation associated with LABA-LAMA-ICS use relative to Tio+Olo use, along with 95% confidence intervals (CI).Current use will be defined based on the days supply during the period of overlap, allowing a grace period of 15 days following the end of days supply to account for intermittent use. This approach allows consideration of exposure as time-dependent, accounting for the changes in exposure during the follow-up. In particular, this analysis excludes patients stopping one or more of the drugs prior to the index date.

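### The discontinuation rule in Section 7.4.1 is not tied to the index drug, so a reliever fill can keep a patient in the exposed segment, in conflict with Section 7.9.1

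*Combined protocol and SAP*

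**What the plan says.** Section 7.4.1 opens by saying that the as-treated main analysis "will consider continuing exposure of the initial treatment of Tio+Olo or LABA/LAMA/ICS", measured by days supply with a permitted gap of 15 days. It then lists three events, the earliest of which ends the treatment segment:

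- Rule 1, discontinuation: 15 days after the supply received on the index date runs out "without a subsequent dispensing of COPD medication".
- Rule 2, escalation, for Tio+Olo only: "addition of ICS to Tio+Olo".
- Rule 3, switch: "Any other change in use of study medication by active ingredient, inclusive of a change to a different combination therapy". It also names a move between fixed and free forms and a step down to monotherapy.

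The abstract (Population) ends follow-up at "discontinuation of COPD treatment", and Section 7.3 uses the same expression. Section 7.9.1, which describes the primary Cox model, takes a narrower line: "Current use will be defined based on the days supply during the period of overlap", plus a 15-day grace period. The pneumonia analysis follows a similar as-treated approach.

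**The concern.** The rule that closes a segment decides which person-time and which events are credited to each treatment. Rule 1, Section 7.3 and the abstract use broad wording about COPD medication or treatment in general. The opening of 7.4.1 and Section 7.9.1 use narrow wording about the treatment started at index. For some patients the two give different censoring dates. If the broad wording is programmed, time and events after the index drug has stopped are counted as exposed in both the primary and the pneumonia analysis. The planned sensitivity analysis would not show this. It varies only the length of the gap, and the section it cites, 7.9.2, is in neither the table of contents nor the text.

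**Working it through.** The documents give no figure for off-drug time, so the main check is textual.

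**Which drugs each rule covers.** Rule 3 refers to study medication, and 7.4.1 points to Annex 3.1 for the codes. Annex 3.1 lists single LABA, LAMA and ICS products, LABA/LAMA combinations and a fixed triple. Short-acting beta-agonists, ipratropium and methylxanthines are coded in Annex 3.3 as covariates. Rule 1 says *COPD medication*, with no definition and no code list.

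**Patterns after the index supply ends on day T.**

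| Pattern | Rule 1 | Rule 2 | Rule 3 | Opening of 7.4.1 and 7.9.1 |
|---|---|---|---|---|
| No further respiratory fill | ends at T + 15 | no | no | ends at T + 15 |
| ICS added to Tio+Olo | not met | ends | not needed | index treatment changed |
| Another LABA, LAMA, ICS or combination | not met | no | ends | index treatment changed |
| Only a short-acting bronchodilator or methylxanthine | not met if it counts as COPD medication | no | no | ends at T + 15 |
| Free triple, one component not refilled | not met while the others are filled | no | met, but no date given | overlap ends, plus 15 days |

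The fourth and fifth rows are the problem. In the fourth, the literal list gives no end date while the narrow definition gives T + 15. The main analysis stops at one year, so the disputed time for one such patient can be as long as 365 − (T + 15) = 350 − T days. The sensitivity analyses that use all available data have no such cap.

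In the fifth row the date could be the end of the lapsed supply, that date plus 15 days, or the next fill of the remaining drugs. Rule 1 does not help. It runs from the medication received on the index date, and under Section 7.3 the triple index date can arise from overlapping dispensings, so the drug received that day may be only one component.

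**Why no bias figure follows.** Both illustrations use assumed inputs and crude hazard averages. The value 0.85 is borrowed from the power statement in Section 7.7.

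- Assume on-drug hazards of 0.85 and 1.00, and an off-drug hazard of 1.00 in both arms. With a share f of counted time off drug in the lower-hazard arm, the ratio is 0.85(1 − f) + f. For f = 0.10, 0.25 and 0.40 it is 0.865, 0.8875 and 0.91, which is toward 1.
- Keep the on-drug hazards, assume an off-drug hazard of 1.3 in both arms, and let the off-drug shares be 10% and 40%. The arm hazards are 0.85 × 0.90 + 1.3 × 0.10 = 0.895 and 1.00 × 0.60 + 1.3 × 0.40 = 1.12. The ratio is 0.895 / 1.12 = 0.80, which is away from 1.

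The direction therefore turns on off-drug hazards and arm-specific shares that the documents do not give.

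**The case against.** The best defence is that the plan's own usage closes most of the gap. Section 7.4.3 lists previous COPD treatments as LAMA, LABA, ICS and their combinations, and puts short-acting drugs and methylxanthines under a separate heading for other respiratory drugs. On that usage a reliever is not COPD medication, and rules 1 and 3 cover the same classes. Section 7.9.1 also governs the Cox model and already uses days supply plus 15 days.

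Part of this stands. It shows that the literal reading may not be the intended one. But a covariate list is not a definition of the term in rule 1, and nothing says that 7.9.1 overrides the list in 7.4.1. The period of overlap in 7.9.1 also has no clear meaning for Tio+Olo, whose index date is simply its first dispensing.

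A reader might infer that any COPD refill keeps a patient on treatment. The documents do not support that, because fills of other maintenance drugs trigger rule 2 or rule 3. Nor does a free-triple user who drops a component escape the rules. That is a rule 3 change, and only its date is missing.

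**Conclusion.** The point holds as a conflict between stated rules. One censoring rule for the primary and pneumonia analyses contradicts the plan's own as-treated definition for patients who stop the index treatment but fill a respiratory drug outside Annex 3.1. Component loss in free-combination triple therapy has no date. This rests on reading *COPD medication* literally and on taking Annex 3.1 as the list of study medication.

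Two stronger conclusions are tempting. One is that the primary analysis will count off-drug time as exposed. That is not established, because 7.9.1 can be read to exclude it. The other is that the hazard ratio will be pulled toward 1, and more so in one arm. That is not supported either: the documents give no off-drug share, no off-drug hazard and no split between fixed and free triple therapy, and the second illustration moves the other way. Size and direction are unknown. The correction is still worth making before programming, because the wording allows different censoring dates for the same patient.

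**What to change.** These changes concern how person-time in existing claims is classified, not patient care.

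1. In rule 1 of Section 7.4.1, replace *COPD medication* with *the index medication*.
2. For the free-combination comparator, end the segment 15 days after the first of the LABA, LAMA or ICS supplies lapses. This agrees with the period of overlap in 7.9.1 and dates the missed refill.
3. Bring the follow-up wording in Section 7.3 and the abstract into line, and have 7.9.1 refer to the same end date.

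The cost is a few sentences and no new data. Follow-up becomes somewhat shorter and there will be fewer events.
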